H_{0-1} : Patients screened monthly with UDT and followed up with proactive intervention (if clinically indicated) will not have a time to thrombosis that is different than patients receiving physical examination and reactive intervention (if clinically indicated)

H_{0-2} : Patients screened monthly with UDT and followed up with proactive intervention (if clinically indicated) will not have a number of angioplasty procedures that is different than patients receiving physical examination and reactive intervention (if clinically indicated)

H_{0-3} : Patients screened monthly with UDT and followed up with proactive intervention (if clinically indicated) will not have a number of thrombectomy procedures that is different than patients receiving physical examination and reactive intervention (if clinically indicated)

H_{0-4} : Patients screened monthly with UDT and followed up with proactive intervention (if clinically indicated) will not have a rate of tunneled dialysis catheter (TDC) that is different than patients receiving physical examination and reactive intervention (if clinically indicated)

H_{0-5} : Patients screened monthly with UDT and followed up with proactive intervention (if clinically indicated) will not have a rate of non-tunneled dialysis catheter (non-TDC) that is different than patients receiving physical examination and reactive intervention (if clinically indicated)

Sample Size:

$\alpha = 0.05$, $\beta = 0.80$, 2-sided (testing benefit and harm)

Main predictor: Treatment or control; Main outcome: Thrombosis or no—two-sided therefore chi-square for proportions of dichotomous variables was used for sample size calculations.

Treatment versus control estimates of thrombosis (based on Tessitore 2004; Scaffaro 2009, Moist 2003, Robbin 2006, Sands 1999, Ram 2003, Tessitore 2008): 34% in control; 24% in treatment (effect size 30%); 342 per group; loss to f/u (move, transplant, different clinic) 5% = $1/(1-.5)=1.05=359$ (low estimate); loss to mortality 10% a year = 1.11 2x (per [name]) = 443

Variables to be collected at baseline:

age, sex, race (white, black, Asian/Pacific Islander, American Indian/Alaskan Native), ethnicity (Hispanic or not), insurance type (private, Medicaid, Medicare,

Hemodialysis Access Surveillance Evaluation (HASE) Study

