Veterans/Military, uninsured), length of time in dialysis (weeks); diabetic (y/d), CAD, PVD, HTN, how long access has been in place (weeks), location (Right/Left, arm/forearm), type of access (AVF or AVG), other clinical variables, button hole, history previous access (Y/N), history of previous catheter (Y/N), length of catheter placement/use (Days)

Variables to be collected monthly:

Monthly questionnaire.

Statistical Analysis:

- **Step 1:** Descriptive analysis to assess similarity of patients between trial arms and to assess representativeness of study participants to hemodialysis patients (generalizability).
- **Step 2:** Descriptive analysis for primary outcome (chi-square) and secondary outcomes (t-test or non-parametric equivalent)
- **Step 3:** Kaplan-Meier Survival Curve (unadjusted)
- **Step 4:** Survival Time Analysis Cox proportional hazards model (adjusted)
- **Step 5:** Multilevel regression with random effects in a mixed regression model to adjust for potential group-level RN, center, city effects. Primary analysis is a dichotomous variable (y/n). Secondary analysis outcomes continuous but may be treated as categorical variables

Covariates for evaluation in the models: individual-level predictors: age, race, sex, insurance, length of time in dialysis (weeks), diabetes (y/n), CVD (y/n), how long access has been in place (weeks), access location, type of access, location of access , length of time in study before thrombosis or mortality (weeks); other significant clinical variables group-level predictors: RN, dialysis center, city

Cross-overs: intervention participants who do not get clinically indicated treatment will be analyzed in two ways--included in treatment arm (intention-to-treat) and excluded (per protocol)

Statistical monitoring: analysis will be conducted 6 months; 12 months; 18 months; and 24 months. If a clear benefit is identified early or if the intervention is unexpectedly harmful, the study will be stopped early.

Risks to Subjects

Risk from Ultrasound Dilution Technique: UDT is a non-invasive procedure that generates no risk to patients undergoing hemodialysis. We do not anticipate any problems as a result of patients undergoing this procedure.

Risk to Privacy: There may be breach of confidentiality regarding protected health information. To minimize the potential risk to privacy all data are de-identified with use of study specific ID numbers only. To ensure that participants' confidentiality is

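### Step 3 plans a Kaplan-Meier curve for thrombosis with no rule for deaths; at the plan's 10% a year mortality, the usual censoring overstates 2-year risk by about 3 points

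*Combined protocol and SAP*

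**What the plan says.** Time to thrombosis is the first secondary hypothesis. Its null is that surveillance patients "will not have a time to thrombosis that is different than patients receiving physical examination and reactive intervention". Two time-to-event methods are named under Statistical Analysis: Step 3, "Kaplan-Meier Survival Curve (unadjusted"), and Step 4, "Survival Time Analysis Cox proportional hazards model (adjusted").

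Neither step defines the event, gives a censoring rule or says what happens to a patient who dies without thrombosis. No competing-risk method is named. In that section death appears only within the covariate list, in an item for time on study up to thrombosis or death. That item does not say whether a death is an event or a censoring time.

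The Sample Size paragraph expects deaths to be common: "loss to mortality 10% a year", applied for two years. Transplant is listed separately, under "loss to f/u (move, transplant, different clinic) 5"%. The planning proportions are "34% in control; 24% in treatment (effect size 30%); 342 per group".

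The primary outcome is thrombosis yes or no. It is analysed by chi-square in Step 2 and by a multilevel model in Step 5.

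**The concern.** Death prevents a later thrombosis; it does not merely hide one. One minus the Kaplan-Meier estimate with deaths censored is the risk that would apply if nobody died. The primary outcome is the share of real patients who clot. With 10% dying each year, the two quantities differ visibly.

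The trial report would then carry two different 2-year figures for the same outcome, the Step 2 proportion and the Step 3 curve, and the plan would not explain the gap. The Objectives section intends the outcomes to be carried over to cost. That use needs absolute risks, and the absolute risks are what the censored curve overstates.

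Because no rule is written down, the handling of deaths could also be chosen after the data are seen.

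**Working it through.** **Inputs from the plan.** Thrombosis 34% (control) and 24% (treatment), mortality 10% a year and other loss 5% (Sample Size); follow-up 2 years (Inclusion and Exclusion Criteria; Procedures Involved); alpha 0.05, "2-sided (testing benefit and harm"). The 0.80 printed as beta is read as power.

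**Inputs assumed.** Constant hazards, the same mortality in both arms, and death independent of thrombosis. The plan gives none of these.

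**The plan's own figures.** The plan says that "chi-square for proportions of dichotomous variables was used for sample size calculations". The two-proportion formula with continuity correction gives 342 per group, an exact match (323 without the correction). Then 342 × 1.05 = 359, and 359 / 0.9² = 443.2, against the stated 443. So the plan does apply the 10% for two years: 1 − 0.9² = 19% of patients who would otherwise stay event-free.

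**Formulas.** Let h be the thrombosis hazard and d the death hazard per year.
- d = −ln(0.9) = 0.1054
- Proportion that actually clots by 2 years: h/(h+d) × (1 − exp(−2(h+d)))
- One minus Kaplan-Meier with deaths censored: 1 − exp(−2h)

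**Control.** The first expression equals 34% at h = 0.2342. Check: 0.2342/0.3396 × (1 − exp(−0.6791)) = 0.690 × 0.493 = 0.340. The censored curve gives 1 − exp(−0.4684) = 37.4%.

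**Treatment.** The first expression equals 24% at h = 0.1538. Check: 0.1538/0.2591 × (1 − exp(−0.5183)) = 0.593 × 0.404 = 0.240. The censored curve gives 1 − exp(−0.3075) = 26.5%.

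**Range over mortality**, with 34% and 24% held as the proportions that actually clot:

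| Mortality a year | Control, deaths censored | Treatment, deaths censored | Difference |
|---|---|---|---|
| 5% | 35.6% | 25.2% | 10.5 points |
| 10% | 37.4% | 26.5% | 10.9 points |
| 15% | 39.3% | 27.9% | 11.4 points |
| 20% | 41.3% | 29.4% | 12.0 points |

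The overstatement runs from 1.6 to 7.3 points in control and from 1.2 to 5.4 points in treatment.

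**Other reading of the planning figures.** If 34% and 24% are themselves Kaplan-Meier risks, then h = −ln(0.66)/2 = 0.2078 and −ln(0.76)/2 = 0.1372. The proportions that actually clot are then 30.9% and 21.7%, so the gap is of similar size.

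**Other codings of death.** In a simulation of 1,000,000 patients per arm, keeping deaths in the risk set as event-free to 24 months gave 34.0% and 23.9%, equal to the simulated crude proportions. With 5% independent loss added it gave 33.9% and 23.9%. Counting deaths as events gives 1 − exp(−2(h+d)) = 49.3% and 40.4%, which is the risk of thrombosis or death, a different endpoint.

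**The case against.** The case for leaving Step 3 alone is that it is one unadjusted curve supporting a secondary hypothesis. The observed proportions come from Step 2, and the primary outcome is binary. A Cox or log-rank comparison with deaths censored is a legitimate comparison of cause-specific hazards. The arm comparison barely moves: the difference shifts by 0.9 points, against a standard error of √((0.34 × 0.66 + 0.24 × 0.76)/225) = 4.3 points if 450 patients split evenly, ignoring clustering and loss. The risk ratio is 0.708 on the censored curve against 0.706. All of this stands, and it limits the weight of the point. It does not remove the overstated absolute risks.

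A reader might infer three stronger things that the documents do not support.

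- *That the curve must be wrong whatever is done with deaths.* The plan states no coding, and holding deaths event-free to 24 months reproduces the right curve. The finding is a missing rule whose usual default misstates the risk.
- *That a mortality difference between arms would secretly distort the Kaplan-Meier comparison.* With independent hazards the censored curve contains no death term. With h = 0.2078 in both arms and mortality of 5% against 15% a year, it reads 34.0% in both, while cumulative incidence reads 32.4% and 29.4%. Distortion would need death and thrombosis to be dependent, and the plan gives nothing with which to size that.
- *That power is lost.* That follows only if deaths are counted as events. The plan does not propose this, and its hypothesis concerns time to thrombosis.

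**Conclusion.** The concern holds as a gap in the secondary time-to-event analysis that should be closed. Step 3 names Kaplan-Meier, gives no rule for deaths, and sits in a plan that expects about 19% mortality over follow-up. Applied in the usual way, it would overstate the 2-year risk of thrombosis by about 3.4 points in control and 2.5 points in treatment, and the arm difference by 0.9 points.

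These sizes rest on constant, equal and independent mortality, and on reading 34% and 24% as the proportions that actually clot. The statement that the curve will not match the primary outcome further assumes that a patient who dies without thrombosis is counted as having had none; the plan does not say this either. The effect is on displayed absolute risk. It gives no reason to doubt the primary binary test or the Cox hazard comparison.

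**What to change.** In the Statistical Analysis section:

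1. Replace Step 3 with cumulative-incidence (Aalen-Johansen) curves by arm for first thrombosis, treating death and transplant without thrombosis as competing events.
2. State that the Step 4 Cox model estimates the cause-specific hazard of thrombosis, with competing events censored at their date.
3. Show the cumulative incidence of death by arm beside the thrombosis curves. This is needed because a cumulative-incidence curve for thrombosis also depends on mortality, so an arm with more deaths can appear to clot less.

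The cost is a few lines of text, one standard routine and a little more analysis work. Dates of death and exit are needed for follow-up time in any case. The reported absolute risks will be slightly lower than on a death-censored curve. Sample size and trial conduct do not change.

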- b. Patients will be referred for an intervention if clinical indication is met. Clinical indications include prolonged bleeding for more than 30 minutes (cannot be explained by medication), upper extremity edema, difficult cannulation, aspiration of clots during cannulation, aneurysmal formation. Access pressure that prevents normal HD machine operation (such as high venous pressure [>250 mm Hg] on three or more consecutive dialysis treatments, negative arterial pressure [<-250 mm hg] on three or more consecutive dialysis treatments). Any Kt/V that cannot be explained by other factors and high recirculation rate of more than 10% would be checked by Transonic Recirculation/flow test prior to referral (rear event).

Control group

Control group will receive standard monitoring (standard care). Standard monitoring is physical examination by a qualified individual (nurse) at each dialysis encounter. Patients will be referred for an intervention if clinical indication is met. Clinical indications include prolonged bleeding for more than 30 minutes, low Kt/v that cannot be explained by other factors, high venous pressure (>250 mm hg) on three or more consecutive dialysis treatments, negative arterial pressure (<-250 mm hg) on three or more consecutive dialysis treatments, upper extremity edema, difficulty cannulation, aspiration of clots during cannulation, aneurysmal formation and high recirculation of more than 10%.

Enrollment period

Enrollment period is expected to be 3-6 months.

Transonic measurement protocol:

Access recirculation, access flow would be determined using the ultrasound dilution technique (Transonic system).

1. Within 90 min of the beginning of HD session HD03 sensors are clamped HD tubing lines
2. Recirculation, access flow will be performed according to HD03 Manual.
3. Post intervention evaluation is as per each arm follow up unless other follow up deemed necessary by the interventionalist.

Hemodialysis Access Surveillance Evaluation (HASE) Study

Data Management

Primary Hypothesis:

H_0 : Patients screened monthly with Transonic Ultrasound Dilution Technique (UDT) and followed up with proactive intervention (if clinically indicated) will not have a rate of access thrombosis that is different than patients receiving physical examination and reactive intervention (if clinically indicated).

Secondary Hypotheses:

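### The primary outcome is yes/no thrombosis although about 23% of patients are expected to leave early and no rule says how leavers count; the planned time-to-event analysis should be primary

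*Combined protocol and SAP*

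**What the plan says.** - **Outcome and sizing.** Sample Size takes thrombosis or not as the main outcome and says that "chi-square for proportions of dichotomous variables was used for sample size calculations". Its inputs are "34% in control; 24% in treatment (effect size 30%); 342 per group", and the test is "2-sided (testing benefit and harm").
- **Expected exits.** The same section inflates for 5% loss to follow-up (moves, transplants, changes of clinic) and for "loss to mortality 10% a year", applied twice, reaching 443.
- **Analysis.** Step 2 of Statistical Analysis applies a chi-square to the primary outcome but calls that step descriptive. Step 3 is a "Kaplan-Meier Survival Curve (unadjusted") and Step 4 an adjusted Cox model. Step 5 is a multilevel mixed model, and there the plan states "Primary analysis is a dichotomous variable (y/n").
- **Hypotheses.** The primary null is that the surveillance group "will not have a rate of access thrombosis that is different" from control. Time to thrombosis is secondary hypothesis H0-1.
- **Covariates.** The list of individual-level predictors includes the number of weeks on study up to thrombosis or death.
- **Not stated.** The documents do not say how a patient who dies, is transplanted or transfers before 24 months is classified in the yes/no outcome.

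**The concern.** A yes/no outcome at two years is well defined only for patients observed for two years or until a thrombosis. The plan expects nearly a quarter to leave before then. Two natural rules are open, and each has a cost. If all leavers are dropped, their follow-up and any thrombosis before exit are lost. If they stay in as no thrombosis unless one was recorded, exposure is ignored, and an arm that loses patients faster shows fewer thromboses even when the underlying hazard is the same.

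Unequal exit is possible here because whole dialysis shifts are allocated, so differences in case mix between shifts can carry into the arms. If the rule is chosen after the data are seen, the primary result can depend on that choice.

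**Working it through.** **Inputs from Sample Size:** 34% v 24% thrombosis, two-sided alpha 0.05, power 0.80, 5% loss, 10% mortality a year. From Procedures Involved: two years of follow-up.

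**Assumptions:** 34% and 24% are two-year risks in the absence of death (the plan gives neither horizon nor definition); constant hazards; exit independent of thrombosis; equal arms; no clustering.

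**The plan's own figures.** The two-proportion formula with continuity correction gives 342 per group, an exact match (323 without the correction). Then 342 x 1.05 = 359, and 359 / 0.81 = 443.

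**Expected early exit.** 1 - 0.95 x 0.90 x 0.90 = 23.05%. From the plan's own sizes, 1 - 342/443 = 22.8%.

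**Hazard ratio.** ln 0.76 / ln 0.66 = 0.66.

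**Thrombosis seen before exit.** With annual thrombosis hazard h and exit hazard m, the two-year proportion is h/(h+m) x (1 - exp(-2(h+m))). With h = -ln 0.66 / 2 or -ln 0.76 / 2, and m = -ln 0.7695 / 2, it is 30.2% v 21.2%. At 443 per arm this gives 443 x (0.302 + 0.212) = about 228 events; at 225 per arm, about 116.

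**Power with equal exit**, from formulas and simulation:

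| Handling | 443 per arm | 225 per arm |
|---|---|---|
| Drop all leavers | 82% | 54% |
| Ever/never, all randomised | 86-87% | 58-59% |
| Time to event | 88% | 60-61% |

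The first row is the chi-square on 443 x 0.7695 = 341 or 225 x 0.7695 = 173 completers per arm. The third is Schoenfeld's formula: sqrt(228)/2 x 0.415 - 1.96 = 1.17, or 88%.

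**False positives with no treatment effect** (34% two-year risk in both arms, 5% other loss in each; simulated):

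| Assumed annual mortality by arm | Expected ever thrombosed | Ever/never, 225 per arm | Ever/never, 443 per arm | Log-rank |
|---|---|---|---|---|
| 10% v 10% | 30.2% v 30.2% | 5% | 5% | 5% |
| 10% v 13% | 30.2% v 29.3% | about 5.5% | about 6% | 5% |
| 10% v 20% | 30.2% v 27.2% | about 11% | about 16% | 5% |

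Dropping every leaver, whatever the outcome, keeps false positives near 5% throughout, at the lowest power.

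**Absolute risk.** With death alone competing (m = -ln 0.90 a year), the same formula gives 30.9% and 21.7%, where one minus Kaplan-Meier gives 34% and 24%. A Kaplan-Meier curve therefore should not be read as the proportion who will have a thrombosis.

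**Time on study as a covariate.** This does not correct for unequal follow-up. A thrombosis ends the count of weeks, so the outcome partly determines the covariate, and adjusting for it can bias the treatment estimate.

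**The case against.** Much of the case on the other side stands.

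- **Power.** A reader might infer that the binary outcome leaves the trial short of its stated 80%. It does not: the inflation to 443 covers these losses, and even dropping all leavers keeps 82%. The low figures at 225 per arm come from the separate conflict between 443 per group and 450 in total. If 450 means completers, as Recruitment Methods suggests, 225 completers per arm give about 65%.
- **Headline test.** A reader might take the Step 2 chi-square as the primary test. The plan calls that step descriptive and puts its primary-analysis sentence in the Step 5 mixed model. Both are binary, so the point holds on either reading.
- **Exclusion of leavers.** Inflating a sample size does not show that leavers with a recorded thrombosis will be dropped. No section says so.
- **Bias.** The 11% and 16% need mortality to double in one arm. Shifts alternate from a random start within each clinic, so imbalance favours neither arm systematically.
- **Log-rank is not immune.** In an assumed extreme case (10% v 60% frail patients, frailty tripling death and raising thrombosis 1.5-fold), unadjusted log-rank gave roughly 20% false positives and ever/never roughly 10%. The arms then differ in thrombosis risk itself, which calls for baseline adjustment.
- **Choice of estimand.** Ever/never among all randomised is close to the cumulative incidence with death competing, which is a legitimate quantity. It answers a different question from the hazard of thrombosis while at risk.
- **Wording.** The word rate in the primary null is weak evidence, since H0-4 and H0-5 use it loosely too.

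**Conclusion.** The concern holds in a limited form. The primary outcome is binary, about 23% of patients are expected to leave early, and no rule classifies them. Time to event is better by about 6 points of power than dropping leavers, and by 1 to 2 points than ever/never. Its main advantage over ever/never is that the comparison does not move with exit rates, provided exit is unrelated to thrombosis risk given the covariates.

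It would be too strong to say that the planned result will be biased. That requires materially different exit between arms, and the documents give no exit rates by arm. With equal exit every method holds 5%, and a modest gap makes almost no difference. All figures ignore clustering by shift. Time to thrombosis is already a stated hypothesis with planned methods, so the change is a promotion from secondary to primary, worth making before outcome data are seen.

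**What to change.** 1. Make time from randomisation to first access thrombosis the primary outcome. Use a Cox model over all randomised patients, with the planned baseline covariates, stratified by clinic and accounting for clustering by shift. Censor at death, transplant, transfer or 24 months.
2. Remove time on study from the covariate list.
3. Report the 24-month cumulative incidence by arm, with death and transplant as competing events.
4. Keep the binary analysis as supportive, counting every thrombosis observed before exit, and state how leavers are classified.
5. Tabulate exits by arm and reason.

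**Cost.** SAP wording, some programming for the clustered Cox model and the competing-risk estimate, and an event-based restatement of the sample size (183 events by Schoenfeld's formula at a hazard ratio of 0.66, before clustering). Event and exit dates are needed for the planned Kaplan-Meier curve anyway. The headline becomes a hazard ratio, so the 24-month risks should stand beside it. The conflict between 443 per group and 450 in total must be resolved separately; this change does not repair it.

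### Time in study until thrombosis or death is listed as a predictor; it cannot be fitted in the Cox model and would weaken or break the Step 5 yes/no model

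*Combined protocol and SAP*

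**What the plan says.** All references are to the combined protocol and SAP. Under Statistical Analysis, Step 4 is a "Survival Time Analysis Cox proportional hazards model (adjusted") and Step 5 is a "Multilevel regression with random effects in a mixed regression model" for group-level effects. Step 5 adds: "Primary analysis is a dichotomous variable (y/n").

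One list then serves these models. It opens "Covariates for evaluation in the models: individual-level predictors: age, race, sex, insurance" and later includes "length of time in study before thrombosis or mortality (weeks"). The same list separately names time on dialysis and age of the access, so the item is not a loose name for either. Nothing in the document calls it a time axis, an exposure or an offset, or confines it to one step.

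The Primary Hypothesis says that patients under surveillance "will not have a rate of access thrombosis that is different". The first secondary hypothesis (H0-1) says that they "will not have a time to thrombosis that is different than patients receiving physical examination". The Sample Size section assumes "34% in control; 24% in treatment (effect size 30"%), with 10% mortality a year and 5% loss to follow-up.

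**The concern.** A covariate in a treatment comparison should be fixed before randomisation. This one is the length of the patient's own follow-up, which ends because of thrombosis or death. It therefore carries the outcome.

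In the Cox model the time to the event would be used to predict the time to the event. In the yes/no model, reaching week 104 free of thrombosis means a no by definition, while most earlier leavers are a yes. The term then explains much of the outcome that the arm comparison is meant to explain. Step 5 matters because it is the only step with random effects, in a trial randomised by shift, and because the words about the primary analysis appear there.

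**Working it through.** **Inputs from the plan (Sample Size; Number of Subjects; Inclusion criteria).** Two-year thrombosis 34% control and 24% surveillance; two-sided 0.05; power 0.80 (printed as beta); 10% mortality a year; 5% loss; two years of follow-up, taken as 104 weeks. The size section arrives at 443 on a per-group basis, while the stated total is 450 (225 per arm), so both were run.

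**The plan's own figure.** Two proportions, no continuity correction: (1.960 × √(2 × 0.29 × 0.71) + 0.842 × √(0.34 × 0.66 + 0.24 × 0.76))² / 0.10² = 322.04, rounded up to 323. With continuity correction: (322.04/4) × (1 + √(1 + 4/(322.04 × 0.10)))² = 342, as stated. Then 342 × 1.05 = 359 and 359/0.9² = 443.

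**Cox model (Step 4).** At each event time the patient who fails has the smallest follow-up time in the risk set. Making the time coefficient more negative can therefore only raise the partial likelihood, and there is no finite maximum. No hazard assumption is needed. In one simulated trial the partial log-likelihood was -1095.5 at coefficient 0, -306.9 at -1, -227.7 at -5 and -224.87 at -50.

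**Yes/no model (Step 5), deaths and losses kept as non-events.** Assumption: constant hazards. Per year these are:
- thrombosis, control: -ln(0.66)/2 = 0.208
- thrombosis, surveillance: -ln(0.76)/2 = 0.137
- death: -ln(0.90) = 0.105
- loss: -ln(0.95)/2 = 0.0256

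Proportion leaving before week 104: control 1 - exp(-2 × 0.339) = 0.492; surveillance 1 - exp(-2 × 0.268) = 0.415. Proportion observed to thrombose: control 0.492 × 0.208/0.339 = 0.302; surveillance 0.415 × 0.137/0.268 = 0.212. Share of early leavers who thrombosed: (0.302 + 0.212)/(0.492 + 0.415) = 57%.

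Without the time term the OR is (0.212/0.788)/(0.302/0.698) = 0.62. At 443 per arm the standard error of its log is √(1/(443 × 0.302 × 0.698) + 1/(443 × 0.212 × 0.788)) = 0.156. Power is about Φ(0.472/0.156 - 1.96) = 86%. At 225 per arm the standard error is 0.218 and power is 58%.

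With time as a linear term, simulation gives an OR of about 0.65 and standard errors of about 0.184 (443) and 0.260 (225). Power is then about Φ(0.431/0.184 - 1.96) = 65% and Φ(0.431/0.260 - 1.96) = 38%.

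Simulated power (logistic model, Wald test):

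| Per arm | Without | With | Loss, points |
|---|---|---|---|
| 225 | 58.5% | 37.7% | 21 |
| 342 | 76.0% | 52.9% | 23 |
| 443 | 86.4% | 64.2% | 22 |

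A separate simulation at 225 per arm gave 58.7% and 39.5%, a loss of 19. Reading 34% and 24% as proportions observed after deaths gave 80.5% and 55.9% at 342, a loss of 25. Hence 19 to 25.

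**Sensitivity, loss in points (225 / 443 per arm).**
- Weibull shape 0.6 with 5% mortality: 32.3 / 40.1
- Weibull shape 2.0 with 20% mortality: 4.3 / 5.0
- Follow-up in whole weeks: 19.7 / 23.4
- Random intercept by shift (36 shifts assumed, 400 trials, Monte Carlo error up to 2.5 points): between-shift SD 0, 20.8 / 25.5; SD 0.25 (assumed), 21.0 / 18.5

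**Type I error.** With 29% thrombosis risk and equal mortality in both arms, rejection with the term was 5.0% to 6.2%. With an assumed 10% versus 13% mortality a year it was 11.1% (225) and 14.0% (443), against 6.3% and 6.1% without the term.

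**Offset reading.** Comparing person-time rates gave power of 59.7% (225) and 87.6% (443), so follow-up used as an offset costs nothing.

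**Deaths and losses excluded.** Every remaining non-event has 104 weeks and every event has fewer. Time separated the outcome completely in 1000 of 1000 simulated trials, so the logistic model has no finite estimate.

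**The case against.** The strongest reply is that the plan does not commit to fitting the term. The list is of covariates for evaluation, pooled over models. Step 4 needs follow-up time as its time variable, and the primary null speaks of a rate, so the authors may have listed it for either purpose. That stands as a likely explanation. It does not cure the text, which says predictor, and a data-driven screen would tend to keep a variable so strongly tied to the outcome.

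A second reply is that the Cox failure would be noticed at once. That also stands, so any arm effect printed beside a diverging coefficient should not be counted as a further harm; nobody would report that fit.

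A reader might infer three stronger things that the documents do not support:
- That the trial's main test is compromised. The trial is sized on a chi-square, and Step 2 assigns the chi-square to the primary outcome without covariates.
- That the Step 5 loss is always silent. It is silent only if deaths and losses stay in as non-events. The sample size is inflated for both, which could mean that they are to be excluded, and then the model fails visibly.
- That the loss is known closely. The documents give no hazard shape and no intra-shift correlation.

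**Conclusion.** Wrong as written, and should be fixed. The Cox result follows from the definition of the partial likelihood. The Step 5 loss of about 19 to 25 points rests on the plan's event, mortality and loss figures, a constant hazard, a linear time term, and deaths and losses kept as non-events. Over Weibull shapes 0.6 to 2.0 and mortality of 5% to 20% a year varied together, it is about 4 to 40 points; neither the shapes nor that mortality range comes from the documents.

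The cost is mainly precision. Bias is small (OR about 0.65 against 0.62 to 0.63), and type I error is about 5% to 6% provided mortality is equal in the two arms. The harm is confined to the adjusted analyses in Steps 4 and 5.

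**What to change.** Delete the item from the covariate list. Add a sentence stating that time in study is the time scale of Steps 3 and 4, is not a covariate in any thrombosis model, and enters only as a person-time offset where a rate or count is modelled, for example the angioplasty and thrombectomy counts in H0-2 and H0-3. Keep every baseline covariate already listed.

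The cost is one deletion and one sentence, with no new data. The downside is that the yes/no model will not account for unequal follow-up; the Cox model does.
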